### **1.3.1.2 Pilot Study – Exhausted CD8+ cells predict response to PD-1 therapy in ER+ hormone therapy-resistant breast cancer after epigenetic priming**

Our initial pilot study of 34 patients with ER+ positive patients suggests that vorinostat decreases T-reg with Foxp3 expression. However, these effects were only associated with clinical benefit in patients with high expression of CD8 (CTLA/PD-L1) in their blood or tumor samples.

The pilot included 34 patients (median age 56, 88% ECOG 1) who had been treated with a median of 5 (2-12) prior regimens. A minority experienced grade 3-4 toxicity (autoimmune hepatitis, fatigue, thrombocytopenia), with each toxicity occurring in 2 out of 34 patients (6%). Grade 2 toxicities included fatigue (27%), thrombocytopenia (12%), colitis (3%), and pneumonitis (3%). Six patients did not receive Pembrolizumab due to rapid disease progression or toxicity. 18% (5/28) of patients experienced clinical benefit (defined as CR, PR, or stable disease >6 months). Tumor lymphocyte infiltration and PD-L1 expression were low. High expression of PD-1/CTLA-4 dual staining in CD8 cells (>15% in tumor or blood) was seen in 5 patients, with 80% (4/5) of those patients experiencing benefit, and in one other patient who withdrew from the study in week 3 because of immune hepatitis. 95% (21/22) of patients with less than 20% dual expression had no response. Both tumor and peripheral blood CD8 PD-1/CTLA-4 dual expression strongly correlated with time to progression. Furthermore, reduction in Foxp3+/CTLA-4high Treg population in was seen in most tumors treated with vorinostat, but a more significant reduction Foxp3+/CTLA-4high Treg was seen in responding patients.

All patients in the prior study received vorinostat and pembrolizumab, and it is not clear whether the high response rate in the biomarker-enriched group is due to the biomarker expression

alone or the constellation of the presence of the biomarker in the setting of HDAC inhibitor-induced downregulation of Tregs.

Table 1.1 Duration of Response by percentage of dual positivity of PD-1/CTLA-4 (20%)

[figure not shown]
[figure not shown]

Table 1.2 Duration of Response by percentage of dual positivity of PD-1/CTLA-4 (10%)

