### 8.1 Sample Size Considerations

#### 8.1.1 Sample Size and Power Estimate

For Arm A (pembro + vorinostat + TAM): The null hypothesis that the true response rate for pembrolizumab and vorinostat in ER+ pretreated patients alone without biomarker enrichment is 0.15 which will be tested against the alternative that response rate of pembrolizumab in a biomarker select population is 0.40. In the first stage, 13 patients will be accrued. If there are 2 or fewer responses in these 13 patients, the study will be stopped. Otherwise, 22 additional patients will be accrued for a total of 35. The null hypothesis will be rejected if 10 or more responses are observed in 35 patients. This design yields a type I error rate of 0.025 and power of 0.9 in this treatment arm when the true response rate is 0.4 in this patient subpopulation.

For Arm B (pembro + TAM): The null hypothesis that the true response rate for pembrolizumab in ER+ pretreated patients alone is 0.10 which will be tested against the alternative that response rate of pembrolizumab in a biomarker select population is 0.35. In the first stage, 11 patients will be accrued. If there are 1 or fewer responses in these 11 patients, the study will be stopped. Otherwise, 19 additional patients will be accrued for a total of 30. The null hypothesis will be rejected if 7 or more responses are observed in 30 patients. This design yields a type I error rate of 0.025 and power of 0.9 in this treatment arm when the true response rate of pembro and TAM treatment is 0.35 in this patient subpopulation.

Based on earlier results in Section 1.3 and hypothesized treatment effects, we will most likely to enroll 46 evaluable patients (~65% chance), whereas the possible enrollment ranges from 24 to 65. For the comparison of the treatment arms, the proposed design will have 72.53% power for the Fisher's exact test at 0.1 significance level when the true response rates are 0.4 and 0.1 for the immune priming and the no immune priming treatment arm.

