##### Tumor PD-L1 Assessment

PD-L1 protein expression on tumor tissue from pre-treatment and post-Cycle-3 biopsies and any other tumor biospecimens obtained will be evaluated immunohistochemically and scored on a scale of 0, 1, 2, or 3. This scoring will be used for the determination of relationships between tumor PD-L1 expression and clinical responses described above. Specifically, in addition to hypothesizing that delayed pembrolizumab treatment (i.e., Arm A) will increase tumor response, we hypothesize that (i) PD-L1 expression will stimulate tumor response, (ii) but will not be associated with treatment (because PD-L1 is stimulated by vorinostat, not pembrolizumab).

For analysis, PD-L1 expression level, scored as  $\{0, 1, 2, 3\}$ , will be classified as binary (0 = negative; 1-3 = positive); across two time-points, this defines four types of PD-L1 participants:  $\{0, 0; 0, 1; 1, 0; 1, 1\}$ . We will use logistic regression to estimate Cycle-6 tumor response rate (95% CI) as a function of study arm and PD-L1 level at baseline and Cycle 3. Either time-point will be eliminated from the model if its effect is weak ( $p > 0.2$ ), leaving two types of PD-L1 participants: either  $\{0, 0; 1, 1\}$  or  $\{0, 0; 0, 1\}$ .

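### The exploratory PD-L1 logistic model has no provision for separation, its p > 0.2 rule can delete a perfect predictor if p is a Wald p-value, and the groups it says remain are wrong

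*Combined protocol and SAP*

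**What the plan says.** Section 8.3.4.1, Tumor PD-L1 Assessment, sets out the model: "We will use logistic regression to estimate Cycle-6 tumor response rate (95% CI) as a function of study arm and PD-L1 level at baseline". PD-L1 at Cycle 3 is the third term. The 0 to 3 score "will be classified as binary (0 = negative; 1-3 = positive"), so two time-points give four patterns, written here as 00, 01, 10 and 11 (baseline first).

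The reduction rule follows: "Either time-point will be eliminated from the model if its effect is weak", defined as p > 0.2, "leaving two types of PD-L1 participants: either" {0,0; 1,1} or {0,0; 0,1}.

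The section does not name the estimation method or the test behind p. It does not say what happens under separation, if both time-points are weak, or if one biopsy is missing.

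The data available to this model come from section 8.1.1. For Arm A: "If there are 2 or fewer responses in these 13 patients, the study will be stopped". For Arm B: "If there are 1 or fewer responses in these 11 patients, the study will be stopped". The expected result is stated as: "we will most likely to enroll 46 evaluable patients (~65% chance), whereas the possible enrollment ranges from 24 to 65". On PD-L1 itself, section 1.3.1.2 says of the pilot only this: "Tumor lymphocyte infiltration and PD-L1 expression were low".

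**The concern.** The plan itself expects a small data set with very few Arm B responders, and it reports low PD-L1 expression in the pilot. Ordinary logistic regression breaks down in such data. If every patient in a category has the same outcome, the maximum-likelihood coefficient runs to infinity. Its standard error grows even faster, so the Wald statistic falls towards zero. A rule that deletes terms with large p-values can then delete a term because it predicts perfectly.

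The section hypothesizes that PD-L1 expression promotes response, and this model is where that is examined. A time-point could be reported as weak for numerical reasons alone. Separately, the interval for Arm B could be meaningless, and a reader could not tell which patients are compared after a term is dropped. Quoting an ordinary 95% interval after selecting terms by p-value also ignores the selection.

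**Working it through.** **1. The plan's own figures.** Inputs are the two stage-1 rules in section 8.1.1 and its true rates of 0.4 (Arm A) and 0.1 (Arm B).

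- Arm A continues: 1 − P(X ≤ 2 | 13, 0.4) = 1 − 0.058 = 0.942.
- Arm B stops: P(X ≤ 1 | 11, 0.1) = 0.9^11 + 11 × 0.1 × 0.9^10 = 0.314 + 0.384 = 0.697.
- P(35 in A and 11 in B) = 0.942 × 0.697 = 0.657. The plan says about 65% for 46 patients, so this reproduces. The range 13 + 11 = 24 to 35 + 30 = 65 also agrees.

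**2. The arm coefficient.** P(0 of 11 | 0.1) = 0.9^11 = 0.314. Given that Arm B stops, this becomes 0.314 / 0.697 = 0.45. With no Arm B responder, the maximum-likelihood arm coefficient is infinite whatever the PD-L1 values. If 20% of paired biopsies were missing at random (assumed), the single responder could be lost too: 0.45 + 0.55 × 0.2 = 0.56. The deletion rule does not apply to arm, so this step concerns the interval only.

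**3. One data set, three tests.** Take N = 46 with 15 responders, where all 6 baseline-positive patients respond. For baseline PD-L1, maximum likelihood gives coefficient 22.4 with standard error 11,904.

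| Test | p | Under p > 0.2 |
|---|---|---|
| Wald | 0.998 | deleted |
| Likelihood ratio | 0.0006 | kept |
| Firth penalized likelihood ratio | 0.0025 | kept |

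**4. How often a PD-L1 coefficient is infinite.** PD-L1 prevalence and the share of paired biopsies are not in the documents, so both were varied in simulation (3,000 trials per scenario, two-stage rules applied). Assumptions: baseline prevalence 0.1, 0.2 or 0.4; P(Cycle 3 positive) = 0.7 if baseline positive, otherwise 0.3 in Arm A and 0.1 in Arm B; odds ratio 1, 3 or 10 per time-point; 70% or 100% paired biopsies; Cycle-6 response equal to the stage response. A coefficient was counted as infinite if it exceeded 8 in absolute value or its standard error exceeded 20.

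| Baseline prevalence | True rates 0.4 / 0.1 | True rates 0.4 / 0.35 |
|---|---|---|
| 0.1 | 27–67% | 11–66% |
| 0.2 | 8–52% | 1.5–37% |
| 0.4 | 4–38% | 0.5–18% |

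The Wald p exceeded 0.2 for every infinite coefficient.

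**5. Effect on the deletion rule.** Share of trials that keep baseline PD-L1 (true odds ratio 10, rates 0.4 / 0.1):

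| Prevalence, paired biopsies | Wald | Likelihood ratio | Firth |
|---|---|---|---|
| 0.1, 70% | 14% | 59% | 49% |
| 0.2, 100% | 54% | 83% | 79% |
| 0.4, 100% | 77% | 91% | 90% |

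A second simulation took the 35/11 path with at most one Arm B responder. With 80% paired biopsies, positivity of 10% at baseline and 20% at Cycle 3, and odds ratio 10, Cycle-3 PD-L1 was dropped in 60% of trials by Wald, 20% by likelihood ratio and 24% by Firth. With odds ratio 3 and positivity 20% / 40%, the figures were 48%, 45% and 48%.

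**6. The remaining groups.** This step needs no assumption. Dropping a covariate pools patterns and keeps every patient.

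| Dropped | Groups compared | Pairs the plan lists |
|---|---|---|
| Cycle 3 | {00, 01} v {10, 11} | {00; 11} |
| Baseline | {00, 10} v {01, 11} | or {00; 01} |

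Neither listed pair matches either pooling, and each leaves two of the four patterns unassigned.

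**The case against.** **The test is not named.** The deletion failure needs a Wald p-value, and the plan does not say it will use one. This stands: with a likelihood-ratio p, most of the excess deletion disappears, and likelihood ratio keeps slightly more than Firth in all three settings of step 5. But then whether a perfect predictor is kept turns on a choice the plan leaves open. A likelihood-ratio test also does not repair the infinite estimates or the group definitions.

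**Frequency rests on assumptions.** The pilot's 'low' has no cut-off attached. This trial selects on a T-cell biomarker, counts any score from 1 to 3 as positive, and cites induction of PD-L1 by HDAC inhibitors (section 1.3.1.1). Prevalence could be well above 0.1. This stands, and is why only a range is given.

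**The endpoints differ.** Stage-1 stopping uses 24-week status (section 8.3.2); Cycle 6 falls at about week 18 (section 6.1). A patient stable at week 18 may progress by week 24, so 0 of 11 at stage 1 need not be 0 of 11 here. The 45% rests on treating the two as equal.

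**The response rate can still be computed.** Under separation the fitted rate is finite, for example 0 of 11. What fails is the Wald interval.

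**Stronger readings.** A reader might infer that the rule throws out the strongest predictors in general. The results do not support that: with no true effect and rates 0.4 / 0.1, 28–49% of infinite baseline coefficients also have likelihood-ratio p > 0.2 (50–78% by Firth), so many reflect a few positive patients and nothing more. A reader might also infer that patients are removed from the analysis. The plan excludes nobody; the list of types is a wording error.

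**Conclusion.** The point holds as a minor one.

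- **Certain from the text:** no test is named, separation is not handled, and the listed types are inconsistent with dropping a time-point.
- **Arm interval:** on the most likely path (0.657) the maximum-likelihood arm coefficient is infinite in 45% of cases. This assumes an Arm B rate of 0.1 and Cycle-6 response equal to stage-1 response.
- **Deletion of a perfect predictor:** this follows if p is a Wald p-value. The frequency cannot be fixed from the documents; 0.5% to 67% is the span over assumed scenarios. The choice of test matters greatly at odds ratio 10 with low positivity and hardly at all at odds ratio 3 with 20% / 40%.

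The analysis is exploratory. No primary or secondary conclusion and no stopping rule depends on it.

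**What to change.** In section 8.3.4.1, Tumor PD-L1 Assessment:

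1. Specify Firth penalized (or exact) logistic regression, with profile-likelihood 95% intervals and, for Firth, penalized likelihood-ratio p-values.
2. Delete the p > 0.2 elimination. Report the pre-specified model with arm and both time-points. Add single time-point models as supportive analyses, each using every patient with that biopsy.
3. Delete the sentence on the remaining types, or replace it with the groupings in step 6 and state that all patients are retained.

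The cost is a few lines of text and standard software, with no new data or patients. Two things are given up: the data-driven simplification, and a little shrinkage. In a single group with 0 of 11 responders, Firth gives (0 + 0.5) / (11 + 1) = 4.2% where maximum likelihood gives 0%. The observed counts by arm and PD-L1 pattern should be shown beside the fitted rates.

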##### Tissue Immune Subset Quantification and Localization

For all subjects, immune cell subsets and localization will be summarized by changes from baseline to after treatment using descriptive statistics.

##### Immune Cell mRNA Signatures of Response

To identify individual genes whose expression levels at pre-treatment are associated with pCR, we will apply two-sample t-tests to compare responders and non-responders. Adjusted P values controlling for false discovery rate (Benjamini and Hochberg method) will be derived. In addition, to assess association of pre-specified immune gene signature with response, the median expression level of the component genes will be used to represent the signature and two-sample t-tests will be used. For genes or signatures that emerge as significantly associated with response, logistic regression models will be used to assess their independent association with response after adjusting for known clinical prognostic factors. To identify pharmacodynamic markers, paired t-test will be carried out to examine immune gene expression differences between pre-treatment and post-treatment samples. Additionally, association of gene expression levels after epigenetic priming with long-term efficacy outcomes, such as PFS and

DFS, will be explored using the Cox proportional hazards regression model. Hierarchical clustering superimposed with response status, relevant baseline or prognostic characteristics or experimental factors will be performed using Spearman correlation and complete linkage to visualize the discriminating power of the immune gene expression and the correlative structure among the genes and the samples.

#### T cell Receptor (TCR) Deep Sequencing

The change in tumor-infiltrating TCR between pre-treatment and post-epigenetic priming will be assessed by calculating the number of unique clonotypes comprising the top 25th percentile of cumulative reads after sorting by clone abundance. Repertoire change between sequencing experiments will be measured using Morisita's distance. This analysis will also be performed in subjects receiving adjuvant chemotherapy using the same statistical techniques to evaluate the impact of adjuvant MPDL3280A on circulating T cell repertoire remodeling.

#### Genomic Signatures of Response

It is hypothesized that tumors with highly mutated or copy-aberrant genomes will either overexpress native proteins or express novel mutant proteins, both of which may be recognized by the immune system and serve as tumor-specific antigens. Therefore, the effect of genomic mutations on the immune landscape will be investigated in each of the cohorts in this study as follows.

Tumor DNA will be isolated from pre-treatment tissue and post-epigenetic priming specimens and will be analyzed for copy number using the Human Genome CGH 244K Microarray (Agilent, Santa Clara, CA) and/or by next-generation sequencing. Results will be analyzed with DNA Analytics software (Agilent) and with the assistance of the UCSF Genome Core and the UCSF Biostatistics core. For copy number paired Wilcoxon signed-rank test will be applied to test the difference of tumor gene copy number between pre and post-treatment. Two-sample Wilcoxon signed-rank test will be used to test the gene copy number between tumor responders and non-responders for pre-treatment, post-treatment, and changes before and after the treatment, separately. Multiple testing adjustment will be done by controlling false positive rate. Next-generation sequencing will take place using appropriate methods and biostatistical analyses. Annotation will be based on NCBI and UCSC databases. Chi-square test will be applied to obtain the significant variants associated with the clinical response.

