#### Circulating Antibody Detection and Characterization

Spotted antigen arrays will be used to detect circulating antibodies will be performed on sera derived from the pretreatment and after 9 weeks on vorinostat. After standard preprocessing of the protein array data, Cluster and Treeview software will be used for unsupervised clustering of the data with Pearson correlation and complete linkage. For each array, an antigen is identified

as being detected if its value is above the median. To determine the number of up- and down-modulated antibodies, the difference in log2 intensity values of pretreatment and post-treatment samples will be taken for each patient to identify antigens that are detected differentially due to treatment. Number of antibodies with at least 2- or 4-fold difference between pretreatment and post-treatment samples will be compared between clinical responders and nonresponders by performing two-sided Wilcoxon rank sum test.

All correlative studies and assays will be performed in the [name] lab, in conjunction with Merck, with the help of [name] and other experts in the field.

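### Section 8.3.4 names a paired test for independent groups, an unclear multiplicity rule, chi-square without a small-count rule, and pCR and DFS in stage IV disease: minor wording errors to correct before analysis

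*Combined protocol and SAP*

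**What the plan says.** All the instructions are in Section 8.3.4.

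- **Copy number (Genomic Signatures of Response).** For change over time, a "paired Wilcoxon signed-rank test will be applied to test the difference of tumor gene copy number between pre and post-treatment". For the responder contrast, the next sentence says "Two-sample Wilcoxon signed-rank test will be used to test the gene copy number between tumor responders and non-responders". Then: "Multiple testing adjustment will be done by controlling false positive rate". No procedure, level or number of tests is given.
- **Variants (same part).** "Chi-square test will be applied to obtain the significant variants associated with the clinical response". There is no rule for small counts. The multiplicity sentence comes before the sequencing text, so it is unclear whether it covers these tests.
- **mRNA signatures.** The stated aim is "To identify individual genes whose expression levels at pre-treatment are associated with pCR", and later Cox models use PFS and DFS. Here multiplicity is explicit: "Adjusted P values controlling for false discovery rate (Benjamini and Hochberg method) will be derived".
- **Antibody arrays (Section 8.3.4.2).** An antigen is identified "as being detected if its value is above the median". The responder comparison is on a different quantity: "Number of antibodies with at least 2- or 4-fold difference between pretreatment and post-treatment samples will be compared", by a two-sided Wilcoxon rank-sum test.

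The note that opens Section 8.3.4.1 describes the tissue assays as exploratory.

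**The concern.** These analyses are meant to show which patients respond, in an open-label trial whose rationale is patient selection. Four instructions do not work as written.

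1. Signed-rank needs one difference per pair. Responders and non-responders form no pairs.
2. The false positive rate is ordinarily the error rate of a single test. Holding it fixed does not adjust for the number of tests, and the wording conflicts with the FDR rule in the mRNA part.
3. Uncommon variants in 30 to 46 patients give 2x2 tables with expected counts well below 5, where the chi-square approximation is unreliable.
4. Section 3.3.1 requires stage IV, measurable disease, and surgery is not part of study treatment. Neither pCR nor DFS is defined among the response and outcome definitions of Section 7.1.4, whereas PFS is.

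If the text stays as it is, the test, the error rate and the outcome will have to be settled by interpretation, possibly after the data have been seen.

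**Working it through.** **Inputs.** Section 8.3.4 gives no sample size, alpha or power for these tests, so it has no figure of its own to reproduce. Group sizes come from Section 8.1.1: Arm A 13 then 35, Arm B 11 then 30, most likely total 46, range 24 to 65. Assumed, because not stated: alpha 0.05 two-sided, and the variant carrier counts.

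**Check on group sizes.** P(46 enrolled) = P(Arm A continues at 0.40) x P(Arm B stops at 0.10) = [1 - P(Bin(13, 0.4) <= 2)] x P(Bin(11, 0.1) <= 1) = 0.942 x 0.697 = 0.657, against the plan's figure of about 65%. In that scenario Arm A is expected to have 35 x 0.4 = 14 responders, and Arm B, having stopped, has at most 1. So 14 or 15 responders among 46 is reasonable.

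**(1) Signed-rank.** With 10 responders and 25 non-responders the test returns an error. If patients were paired arbitrarily (4,000 simulated trials, assumed shift of 1 SD), type I error stays at 0.044 to 0.049 for both tests, but power is lost:

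| Responders v non-responders | Forced-pair signed-rank | Rank-sum |
|---|---|---|
| 10 v 25 | 0.50 | 0.70 |
| 14 v 21 | 0.67 | 0.77 |
| 7 v 23 | 0.33 | 0.59 |

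**(2) Multiplicity.** Under a per-test 5% rule, expected false positives = null tests x 0.05: 1,000 x 0.05 = 50; 20,000 x 0.05 = 1,000. If FDR was meant, as in the mRNA part, this problem does not arise.

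**(3) Chi-square.** Smallest expected count = responders x carriers / n. Exact size = the sum of hypergeometric probabilities of the tables that the test rejects at 0.05.

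For 46 patients with 14 responders, uncorrected Pearson test:

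| Carriers | Smallest expected count | Rejected when responding carriers number | Exact size |
|---|---|---|---|
| 2 | 14 x 2/46 = 0.61 | 2 | (14 x 13)/(46 x 45) = 0.088 |
| 3 | 14 x 3/46 = 0.91 | 3 | (14 x 13 x 12)/(46 x 45 x 44) = 0.024 |
| 4 | 14 x 4/46 = 1.22 | 3 or 4 | 0.0714 + 0.0061 = 0.078 |
| 5 | 14 x 5/46 = 1.52 | 4 or 5 | 0.0234 + 0.0015 = 0.025 |

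With 4 carriers who all respond, the uncorrected p is 0.0016 and the exact p is 0.0061. With 15 responders instead of 14, the size is 0.101 for 2 carriers, 0.030 for 3 and 0.008 for 4.

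For Arm A alone (35 patients, 14 responders, 5 carriers) the smallest expected count is 14 x 5/35 = 2.0. The test rejects at 0, 4 or 5 responding carriers, so its size is 0.0627 + 0.0648 + 0.0062 = 0.134. With 2 carriers it can never reject, so its size is 0.

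Not every table is sparse. With all 65 patients and 26 responders, the smallest expected count is 26 x 13/65 = 5.2 for 13 carriers and 26 x 20/65 = 8.0 for 20 carriers. Fisher's exact test stayed at or below 0.05 in every table tried.

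**(4) Outcomes.** No arithmetic applies. The sentence that names pCR goes on to compare responders with non-responders. Section 8.3.2 defines status at 24 weeks, and Section 7.1.4 defines PFS. Defined outcomes are therefore available for both roles.

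**Above-median label.** By construction it marks half of the antigens on any array as detected. The share was 50% whether 0%, 10%, 50% or 90% were truly reactive. The tested quantity is the count of 2- or 4-fold changes, which does not use the label.

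**The case against.** The strongest reply is that most of this is loose naming. The copy-number sentence says two-sample, directly after a separately named paired test, and the antibody part uses rank-sum for a responder contrast. The multiplicity sentence announces an adjustment, and Benjamini-Hochberg appears in the same section. The pCR sentence itself turns to responders, and PFS stands beside DFS. A test that cannot be run yields no wrong result. This largely stands: it makes slips the likely explanation and shows what was probably intended. It does not make the text correct.

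On chi-square, the reply is that size above 0.05 depends on the counts chosen. That also stands. It is below 0.05 for 3 or 5 carriers in the 46-patient example, and one more responder takes the 4-carrier size from 0.078 to 0.008. A Yates correction kept size at or below 0.05 in the tables tried, with p = 0.0094 in the four-carrier example. The plan does not say whether a correction would be used, and no variant frequencies are given. What remains is that the uncorrected test is erratic at these counts and nothing in the plan guards against it.

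A reader might go further and infer about 12,200 false positives from the 244K array (244,000 x 0.05). That needs both an unadjusted per-test reading and one test per probe. The plan speaks of gene copy number, allows sequencing as an alternative, and states no number of tests. A reader might also infer that the median rule spoils the antibody results; the fold-change comparison does not depend on it.

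**Conclusion.** The concern holds as one of exploratory methods that are wrong or unreliable as written. Two items need no assumption: the signed-rank test does not fit independent groups, and pCR and DFS do not fit this population. The multiplicity wording is unclear and conflicts with the mRNA part; its size, about 50 false positives per 1,000 null tests, applies only on the literal per-test reading at 5%. For chi-square, the range of 0 to about 0.13 rests on assumed carrier and responder counts, a nominal 0.05 and no continuity correction.

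It would be tempting to conclude that the biomarker results will be wrong. The documents do not support that: correct terms for the first two items stand elsewhere in the same section, and common variants in pooled tables can have adequate counts. Severity is minor. The primary endpoint, the Simon rules and the between-arm comparison are untouched, as is the PD-1/CTLA-4 criterion used for entry.

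**What to change.** Amend Section 8.3.4 before any of these analyses is run:

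- **Copy number:** use the Wilcoxon rank-sum test for responders v non-responders, and keep signed-rank for pre/post change.
- **Multiplicity:** state Benjamini-Hochberg FDR at a named level for both the copy-number and the variant tests, and define the family of tests.
- **Variants:** use Fisher's exact test, at least when any expected count is below 5.
- **Outcomes:** replace pCR with the 24-week response status of Section 8.3.2, and DFS with PFS.
- **Optional:** base the antigen detection label on negative-control or background signal, or drop it.

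The cost is SAP wording and fewer nominally significant markers; no added patients or assays. Fisher's test is conservative for rare variants: with 2 carriers among 46 patients and 14 responders, its smallest possible p is 0.088, so no result could reach 0.05.
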